14.3.4 End of Treatment and Follow-up Tumor Imaging

In participants who discontinue study treatment, tumor imaging should be performed at the time of treatment discontinuation (± 4 week window). If previous imaging was obtained within 4 weeks prior to the date of discontinuation, then imaging at treatment discontinuation is not mandatory. In participants who discontinue study treatment due to documented disease progression and the investigator elects not to implement iRECIST, this is the final required tumor imaging.

For participants who discontinue study treatment without documented disease progression, every effort should be made to continue monitoring their disease status by tumor imaging using the same imaging schedule used while on treatment (every 9 weeks in Year 1 or every 6 months after Year 1) to monitor disease status until the start of a new anticancer treatment, disease progression, pregnancy, death, withdrawal of consent, or the end of the study, whichever occurs first.

14.3.5 Second Course (Retreatment) Tumor Imaging

Tumor imaging must be performed within 10 days prior to restarting treatment with pembrolizumab. Local reading (Investigator assessment with site radiology reading) will be used to determine eligibility.

The first on-study imaging assessment should be performed at 9 weeks (63 days ± 3 days) after the restart of treatment. Subsequent tumor imaging should be performed every 9 weeks (63 days ± 3 days) or more frequently, if clinically indicated.

Per RECIST 1.1, if tumor imaging shows initial PD, tumor assessment should be repeated 4 to 8 weeks later in order to confirm PD with the option of continuing treatment while awaiting radiologic confirmation of progression with the option of continuing treatment while awaiting radiological confirmation of progression in clinically stable patients. Participants who obtain confirmatory imaging do not need to undergo scheduled tumor imaging if it is less than 4 weeks later and may wait until the next scheduled imaging time point, if clinically stable.

Imaging should continue to be performed until disease progression, the start of a new anticancer treatment, withdrawal of consent, death, or notification by the Sponsor, whichever

occurs first. Disease progression may be confirmed 4 to 8 weeks after the first tumor imaging indicating PD, in clinically stable participants.

In participants who discontinue study treatment, tumor imaging should be performed at the time of treatment discontinuation (± 4 week window). If previous imaging was obtained within 4 weeks prior to the date of discontinuation, then imaging at treatment discontinuation is not mandatory. For participants who discontinue study treatment due to documented disease progression, this is the final required tumor imaging.

For participants who discontinue study treatment without documented disease progression, every effort should be made to continue monitoring their disease status by radiologic imaging every 6 months (180 days ± 14 days) until either the start of a new anticancer treatment, disease progression, pregnancy, death, or the end of the study, whichever occurs first.

14.4 Drug Diary

Patient Medication Diary

Patient ID _____

Date _____

Patient Initials _____

Vorinostat Dose _____

Day	Date			Time		Please note any unusual symptoms
	Month	Day	Year	Time	AM/PM	
1						
2						
3						
4						
5						
6						
7						
8						
9						
10						
11						
12						
13						
14						

Date of pill bottle return _____

Nurse Signature _____

14.5 Events of Clinical Interest Guidance Document

Attached as PDF entitled, “Pembrolizumab ECI_Guidance Document Version 5_FINAL_18-Dec-2014”

14.6 Woman of Childbearing Potential (WOCBP) definition

A woman is considered fertile following menarche and until becoming post-menopausal unless permanently sterile (see below)

Women in the following categories are not considered WOCBP:

- Premenarchal
- Premenopausal female with 1 of the following:
 - Documented hysterectomy
 - Documented bilateral salpingectomy
 - Documented bilateral oophorectomy

Note: Documentation can come from the site personnel’s review of the participant’s medical records, medical examination, or medical history interview.

- Postmenopausal female
 - A postmenopausal state is defined as no menses for 12 months without an alternative medical cause.
 - A high follicle stimulating hormone (FSH) level in the postmenopausal range may be used to confirm a postmenopausal state in women not using hormonal contraception or hormonal replacement therapy (HRT). However, in the absence of 12 months of amenorrhea, confirmation with two FSH measurements in the postmenopausal range is required.
 - Females on HRT and whose menopausal status is in doubt will be required to use one of the non-hormonal highly effective contraception methods if they wish to continue their HRT during the study. Otherwise, they must discontinue HRT to allow confirmation of postmenopausal status before study enrollment.

14.7 Immune-Related Response Criteria

INTRODUCTION

Increasing clinical experience indicates that traditional response criteria (e.g., Response Evaluation Criteria in Solid Tumors, Version 1.1 [RECIST v1.1] and World Health Organization [WHO]) may not be sufficient to characterize fully activity in the new era of target therapies and/or biologics. In studies with cytokines, cancer vaccines, and monoclonal antibodies, complete response, partial response, or stable disease has been shown to occur after an increase in tumor burden as characterized by progressive disease by traditional response criteria. Therefore, conventional response criteria may not adequately assess the activity of immunotherapeutic agents because progressive disease (by initial radiographic evaluation) does not necessarily reflect therapeutic failure. Long-term effect on the target disease must also be captured. The immune-related response criteria¹ (irRC) are criteria that attempt to do that by enhancing characterization of new response patterns that have been observed with immunotherapeutic agents (i.e., ipilimumab). (Note: The irRC only index and measurable new lesions are taken into account.)

GLOSSARY

Term	Definition
SPD	sum of the products of the two largest perpendicular diameters
Tumor burden	$SPD_{\text{index lesions}} + SPD_{\text{new, measurable lesions}}$
Nadir	minimally recorded tumor burden
irCR	immune-related complete response
irPD	immune-related progressive disease
irPR	immune-related partial response
irSD	immune-related stable disease
irBOR	immune-related best overall response

BASELINE ASSESSMENT USING irRC

Step 1. Identify the index lesions (five lesions per organ, up to ten visceral lesions and five cutaneous lesions).

Step 2. Calculate the SPD of all of these index lesions:

$$SPD = \sum_i \text{ (Largest diameter of lesion } i) \times \text{ (Second largest diameter of lesion } i).$$

¹ Wolchok JD, Hoos A, O'Day S, et al. Guidelines for the evaluation of immune therapy activity in solid tumors: immune-related response criteria. Clin Can Res 2009;15:7412–20.

POST-BASELINE ASSESSMENTS USING irRC

Step 1. Calculate the SPD of the index lesions.

Step 2. Identify new, measurable lesions ($\geq 5 \times 5$ mm; up to five new lesions per organ: five new cutaneous lesions and ten visceral lesions).

Step 3. Calculate the SPD of the new, measurable lesions.

Step 4. Calculate the tumor burden:

$$\text{Tumor burden} = \text{SPD}_{\text{index lesions}} + \text{SPD}_{\text{new, measurable lesions}}$$

Step 5. Calculate the change in tumor burden relative to baseline and the change in tumor burden relative to nadir.

Step 6. Derive the overall response using the table below.

Overall Response	Criterion
irCR	Complete disappearance of all lesions (whether measurable or not, and no new lesions) confirmed by a repeat, consecutive assessment ≥ 4 weeks from the date first documented
irPR	Decrease in tumor burden $\geq 50\%$ relative to baseline confirmed by a consecutive assessment ≥ 4 weeks from the date first documented
irSD	Criteria for irCR, irPR, and irPD are not met; does not require confirmation
irPD	Increase in tumor burden $\geq 25\%$ relative to nadir confirmed by a consecutive assessment ≥ 4 weeks from the date first documented

irCR = immune-related complete response; irPD = immune-related progressive disease;

irPR = immune-related partial response; irSD = immune-related stable disease.

DETERMINATION OF irBOR

Once a patient has completed all tumor assessments, his/her irBOR may be determined:

Condition	irBOR
At least one irCR	irCR
At least one irPR and no irCR	irPR
At least one irSD and no irCR and no irPR	irSD
At least one irPD and no irCR, no irPR, and no irSD	irPD

irBOR = immune-related best overall response; irCR = immune-related complete response;

irPD = immune-related progressive disease; irPR = immune-related partial response;

irSD = immune-related stable disease.

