8.9 Efficacy Analysis

Responses will be tabulated and objective response (CR+PR) via RECIST 1.1 will be summarized with the point estimate and corresponding exact 95% confidence interval. For patients with prostate cancer PSA response ($\geq 50\%$ decline from baseline), PSA progression ($\geq 50\%$ increase from baseline/nadir) and bone lesions progression on ^{68}Ga -PSMA-11 PET or bone scans (≥ 2 lesions from baseline with confirmatory scans 6 weeks later showing ≥ 2 additional lesions) will be reported. Progression free and overall survival will be estimated using standard Kaplan-Meier curves. The median time-to-event for each endpoint will be estimated along with the corresponding 95% confidence interval. Similar descriptive analyses will be performed using irRC criteria. Endpoints such as quantitative characteristics of humoral immune response will be characterized by their mean and corresponding 95% confidence interval. No statistical comparisons are planned. Analyses will be done separately by each expansion cohort. Patients enrolled in the Dose Finding Phase will be excluded when estimating efficacy for the design of a future trial.

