14.3.3 Tumor Imaging During the Study

The first on-study imaging assessment should be performed at 4 weeks (28 days -7 days) from the date of screening. Subsequent tumor imaging should be performed every 9 weeks (63 days \pm 3 days) or more frequently if clinically indicated. After 18 weeks (126 days \pm 3 days), participants who remain on treatment will have imaging performed every 9 weeks (63 days \pm 3 days). Imaging timing should follow calendar days and should not be adjusted for

delays in cycle starts. Imaging should continue to be performed until disease progression is identified by the Investigator.

Objective response should be confirmed by a repeat imaging assessment. Tumor imaging to confirm PR or CR should be performed at least 4 weeks after the first indication of a response is observed. Participants will then return to regular scheduled imaging every 9 weeks, starting with the next scheduled imaging time point. Participants who receive additional imaging for confirmation do not need to undergo the next scheduled tumor imaging if it is less than 4 weeks later; tumor imaging may resume at the subsequent scheduled imaging time point.

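### Appendix 14.7 has no class for unconfirmed irRC progression, so a first-scan progressor who is never scanned again is tabulated as immune-related stable disease

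*Combined protocol and SAP*

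**What the plan says.** Appendix 14.7 sets the irRC rules. irPD needs a rise in tumour burden of at least 25% "relative to nadir confirmed by a consecutive assessment ≥ 4 weeks from the date first documented". irSD is whatever is left over: "Criteria for irCR, irPR, and irPD are not met; does not require confirmation". The best-overall-response table gives irSD for "At least one irSD and no irCR and no irPR", and gives irPD only for "At least one irPD and no irCR, no irPR, and no irSD". Neither table has an entry for progression seen once and not confirmed, or for a patient who cannot be evaluated.

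Section 8.9 brings these classes into the analysis: after the RECIST 1.1 response, PFS and OS summaries, "Similar descriptive analyses will be performed using irRC criteria", separately by expansion cohort. It gives no event or censoring rule for PFS under either set of criteria. Section 8.1 says missing data are not imputed.

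On whether a second scan will exist, the text points both ways:

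- **Towards no second scan.** In 14.3.3, "Imaging should continue to be performed until disease progression is identified by the Investigator". In 5.9, going on to a confirming scan is at the investigator's discretion and only for clinically stable patients. In 5.6, follow-up after documented progression is by telephone for survival. In 14.3.4, for a patient who stops because of documented progression, if "the investigator elects not to implement iRECIST, this is the final required tumor imaging".
- **Towards a second scan.** Sections 7.1.2.5 and 14.3.1 ask for progression to be verified, with treatment continuing until it is. Section 5.6 lists confirmed radiographic progression among its reasons for discontinuation. In 7.1.6.3, confirmed progression is one of two triggers for survival follow-up.

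**The concern.** Stable disease ought to describe a tumour that was measured and had not grown past the progression threshold. Under 14.7 it also takes in tumours that were measured, had grown past it, and were not measured again. Because irSD is a residual class needing no confirmation, the absence of a scan turns progression into stability.

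The missing scans are unlikely to fall at random. Patients who die or deteriorate quickly after the first rise are the least likely to be scanned again, so the worst outcomes are the likeliest to be misfiled.

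At stake is how the irRC table is read beside the RECIST 1.1 table. Part of any gap between them would come from missing confirmation scans, yet it could be taken for pseudoprogression or delayed benefit. Section 8.4 says the expansion cohorts are meant to inform the next phase, and with about 15 patients each, two misfiled patients are visible.

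**Working it through.** The plan gives no figure on this point to reproduce. The check applies the 14.7 tables literally to short scan sequences and then sizes the result.

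**Step 1. Classification.** Here rise means at least 25% above nadir, and stable means no irRC threshold crossed. Scans are at least 4 weeks apart.

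| Post-baseline scans | Visit classes under 14.7 | irBOR |
|---|---|---|
| rise, no later scan | irSD | irSD |
| rise, rise | irPD, irPD | irPD |
| rise, stable | irSD, irSD | irSD |
| stable, rise, no later scan | irSD, irSD | irSD |
| stable, rise, rise | irSD, irPD, irPD | irSD |

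The first two rows are the defect. The first scans are the same, and the only difference is whether a second scan exists. The patient who lives to be rescanned is irPD; the patient who dies first is irSD.

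In row three the later scan does not bear out the rise, so irSD is a fair result. In row four irBOR is irSD under any sensible rule, because a genuine stable scan came first. What is lost there is the irPD date, which matters only for irRC PFS. For irBOR, therefore, only patients whose first post-baseline scan shows the rise should be counted.

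**Step 2. Denominator.** The efficacy population in 8.3.1 needs one dose and one follow-up evaluation, besides eligibility and registration. One scan showing a rise satisfies the last, so the patient in row one stays in the table.

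**Step 3. Size.** Let k be the number of row-one patients in a cohort of 15 (8.4). The share moved into irSD is k/15. The documents give no value for k, so the values below are assumptions:

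- k = 2: 2/15 = 13%
- k = 4: 4/15 = 27%
- k = 6: 6/15 = 40%

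To show this against sampling error, assume also that 5 of 15 are truly irSD or better, which is 33% (exact 95% CI 12% to 62%). The tabulated figure becomes:

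- k = 2: 7/15 = 47% (21% to 73%)
- k = 4: 9/15 = 60% (32% to 84%)
- k = 6: 11/15 = 73% (45% to 92%)

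irRC objective response does not move, because irSD and irPD are both non-response.

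**Step 4. irRC PFS, conditional only.** Suppose unconfirmed rises were censored at that scan and deaths did not count as events; 8.9 says neither. A simulation took 15 patients, scans every 9 weeks (the interval in 14.3.3), exponential progression times and follow-up capped at 104 weeks, with 1,500 runs per scenario. For assumed true medians of 3, 4 and 6 months, counting every first progression gives a typical Kaplan-Meier median of 18, 18 and 27 weeks. With 25% of progressions unconfirmed and censored it is 27, 27 and 36 weeks; with 50%, it is 36, 45 and 63 weeks. This shows sensitivity to an unwritten rule, not an expected bias.

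**The case against.** The strongest reply is that the protocol expects progression to be verified, so unconfirmed cases may be few. Sections 7.1.2.5 and 14.3.1 keep patients on treatment until verification. Sections 5.6 and 7.1.6.3 refer to confirmed progression. The discontinuation scan in 14.3.4 is waived only when a scan was done in the previous 4 weeks, so it could sometimes serve as the confirming scan. This stands against any claim about frequency: k could be close to zero. It does not supply a rule for the cases that do occur, and no instruction can produce a second scan after death. Section 5.6 also lists any progression as a reason to discontinue, without the word confirmed, so the text is mixed.

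A second reply is that irRC is a supplementary description. Response is estimated on RECIST 1.1 and no comparisons are planned. This stands and limits the reach of the point.

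Three stronger readings are tempting, and the documents do not support them:

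- A reader might infer that 14.3.4 ends required imaging at first progression. It sets two joint conditions: treatment stopped for documented progression, and the investigator not electing iRECIST.
- A reader might infer that stopping without a confirming scan is the usual course. Nothing in the documents shows how common it would be.
- A reader might infer that these patients drop out as irRC progression events. Section 8.9 is silent on events and censoring, and an early death might still count.

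**Conclusion.** The classification rule in 14.7 is wrong as written. A patient with a rise of at least 25% on the first post-baseline scan and no later scan is irSD at that visit and irSD as best response, and no other section corrects this. The path is foreseeable, but its frequency cannot be known from the documents.

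The effect is confined to the irRC best-response table and, depending on rules that 8.9 does not state, irRC PFS. RECIST 1.1 response and PFS, and irRC objective response, are unaffected. The shift of 13%, 27% or 40% of a cohort rests entirely on the assumed k of 2, 4 or 6 in 15. A disease-control rate is not a named endpoint, so the shift is best read as movement between two rows of the table.

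**What to change.** In 14.7:

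- Allow irSD only when the tumour-burden change at that time point is itself below the irPD threshold.
- Classify a rise of at least 25% with no later tumour assessment as irPD, dated to that scan, for irBOR and irRC PFS. At the least, give it a separate unconfirmed-irPD class that is never counted as irSD.
- Where a later scan does not bear out the rise, classify by the later scans, so that true pseudoprogression is not penalised.

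In 8.9, carry the same rule into the irRC PFS event definition and report the number of unconfirmed irPD in each cohort.

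Reconcile the iRECIST named in 14.3.4 with the irRC used in 2.1, 7.1.2.5, 8.9 and 14.7. The interval for confirming progression also needs reconciling: at least 4 weeks in 14.7, at least 6 weeks in 5.9, and 4 to 8 weeks for retreatment in 14.3.5.

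The cost is a few sentences and no extra scans or patients. The downside is that the irRC stable-disease and PFS figures become slightly less favourable.
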